4.1 Dose Escalation Halting Criteria

Prior to dose escalation to the next cohort within a route of administration group (see [Table 1](#)), safety data through 7 days post vaccination of the third dose will be reviewed. Specifically, the Statistical and Data Coordinating Center (SDCC) will provide the cumulative safety data and notify the protocol PI, medical monitor (MM), and DMID Independent Safety Monitor (ISM), that the following criteria have not been met based on a review of the safety data collected in the seven days after the third vaccination of the last participant in the current cohort. Only one cohort will be enrolled at a time, and enrollment will proceed from Cohort A to B; Cohort C to D, and Cohort E to F if the halting criteria described in [Section 9.5](#) are NOT met.

In addition, there will be no progression to the next cohort within a route of administration group if the following dose escalation halting criteria is met:

- The site PI, protocol PI, MM, DMID ISM or local DSMB identify a safety concern that would prompt a review by the DMID DSMB.

If the above dose escalation halting criteria are NOT met, the dose escalation may proceed to the next successive route of administration cohort (see [section 9.6.3](#)).

If any of the above dose escalation halting criteria are met, then escalation to the next successive route of administration cohort will not proceed and the data will be reviewed by the DMID DSMB (see [section 9.6.1](#)). The enrollment for the next cohort may begin when all three of the below requirements are met:

- DMID DSMB recommendation to proceed,
- DMID concurs with the DMID DSMB recommendation to proceed,

- Local DSMB recommendation to proceed.

Upon completion of Cohorts A through F, a scheduled DMID DSMB meeting will be convened to review all the safety data (clinical labs and reported events) collected in the seven days after the third vaccination in each cohort. Progression to Cohorts G, H and I will occur when all three of the below requirements are met:

- DMID DSMB recommendation to proceed
- DMID concurs with the DMID DSMB recommendation to proceed
- Local DSMB recommendation to proceed

As the IND sponsor, DMID retains the final decision-making authority to stop the study at any point.

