7.3.5 VISIT 6 (~1 week post-dose 3 \pm 1 day)

- Confirm ongoing consent prior to performing any study procedures. Conduct eligibility review. Review any AEs or SAEs that have occurred since the last visit as well as update the medical history and concomitant medications as necessary
 - Assess for injection site necrosis within 7 days of vaccination.
 - Assess for urticaria, laryngospasm, bronchospasm, or anaphylaxis determined to be related to vaccine and within 7 days of vaccination.
 - Assess for participants experience facial nerve neuropathy, confirmed by an investigator and determined to be related to vaccine.
- Record oral temperature, pulse, and blood pressure
- Targeted physical examination, if indicated based on review of medical history
- Collect approximately 22 mL of venous blood:
 - 2 mL for clinical safety labs: ALT (also known as SGPT), total bilirubin, and creatinine
 - 2 mL for serum ELISA and neutralization assays
 - 2 mL for ASC assay
 - 2 mL for ALS assay
 - 2 mL for ASC with homing

- 12 mL for cryopreservation of PBMC, for memory B cell (5 mL) and effector T cell assays (7 mL)
- Collect plasma from PBMC tubes
- Collect stool (approximately 4 gm) and saliva (approximately 2 mL) for IgA assay.
- 1-2 gm of stool frozen at $-80^{\circ}\text{C} \pm 15^{\circ}\text{C}$ for future use microbiome studies
- Collect memory aid/reactogenicity information
- Provide stool sample collection container and instructions on how to collect stool sample
- Provide instructions to women participants to avoid pregnancy through the 28 days from receipt of the last dose of vaccine.
- Confirm date and time for Visit 7

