7.3.6 VISIT 7 (~4 weeks post-dose 3 (window ± 3 days)

- Confirm ongoing consent prior to performing any study procedures. Conduct eligibility review. Review any AEs or SAEs that have occurred since the last visit as well as update the medical history and concomitant medications as necessary
 - Assess for injection site necrosis within 7 days of vaccination.
 - Assess for urticaria, laryngospasm, bronchospasm, or anaphylaxis determined to be related to vaccine and within 7 days of vaccination.
 - Assess for participants experience facial nerve neuropathy, confirmed by an investigator and determined to be related to vaccine.
- Record oral temperature, pulse, and blood pressure
- Targeted physical examination, if indicated based on review of medical history
- Collect approximately 17mL of venous blood:
 - 2 mL for clinical safety labs: CBC with differential for WBC, Hg, ANC, platelets; creatinine, albumin, and ALT
 - 3 mL for serum ELISA and neutralization assays
 - 12 mL for cryopreservation of PBMC, for memory B cell (5 mL) and effector T cell assays (7 mL)
 - Collect plasma from PBMC tubes
- Collect stool (approximately 4 gm) and saliva (approximately 2 mL) for IgA assay.
- 1-2 gm of stool frozen at $-80^{\circ}\text{C} \pm 15^{\circ}\text{C}$ for future use microbiome studies
- Provide stool sample collection container and instructions on how to collect stool sample
- Provide instructions to women participants to avoid pregnancy through the 28 days from receipt of the last dose of vaccine.
- Confirm date and time for Visit 8

7.3.7 **VISIT 8 (~12 weeks post-dose 3 (window ±1 week)**

- Confirm ongoing consent prior to performing any study procedures. Conduct eligibility review. Review any SAEs that have occurred since the last visit as well as update the medical history and concomitant medications as necessary, to support an SAE.
- Record oral temperature, pulse, and blood pressure
- Targeted physical examination, if indicated based on review of medical history
- Collect approximately 15 mL of venous blood:
 - 2 mL for serum ELISA and neutralization assays
 - 13 mL for cryopreservation of PBMC, for memory B cell (5 mL) and effector T cell assays (8 mL)
 - Collect plasma from PBMC tubes
- Confirm date and time for Visit 9

7.4 **Final Study Visit**

7.4.1 **VISIT 9 (~6 months post-dose 3, window ±2 weeks)**

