8.2 Laboratory Evaluations

8.2.1 Clinical Laboratory Evaluations

A total of 2 mL blood will be collected for screening clinical labs for the evaluation of eligibility. If screening laboratory results are out of range value, they may be repeated once provided there is an alternative explanation for the out of range value. Participants must have acceptable screening laboratory findings within 7 days prior to enrollment. The acceptable ranges for study eligibility are listed in [Appendix B](#).

For the assessment of safety, a total of 2 mL of blood will be collected for clinical safety labs on visit 7, about 4 weeks after the third dose of vaccine. These include a CBC with differential for WBC, Hg, ANC, Platelet count, creatinine, albumin, and ALT. In addition, 2 mL of blood will be collected at visit 6 (7-days post-third dose of vaccine) for ALT, serum bilirubin, and creatinine. The grading of toxicity for clinical safety lab values that are not in the normal range is

provided in [Appendix C](#).

All women will have a urine pregnancy test performed during screening and a urine pregnancy test on the vaccination days. The results of the urine pregnancy test must be negative prior to enrollment in the study, and prior to each vaccination.

For those laboratory tests run as part of a panel of tests, but not required by the protocol, the site is required to do the following:

- Enter all non-required lab results into the database in the comments section of the eCRF.
- When a result is abnormal per the site normal laboratory reference range, the result must be:
 - Entered in the comments section of the database including assessment for clinical significance by site PI,
 - An AE generated and followed until resolution if clinically significant based on assessment by the site PI,
 - If clinically significant, graded according to either the toxicity tables in [Appendix C](#) or if a grading scale is not available, the PI should use the guidance for AE grading.

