9.5 Halting Rules

Further dosing of any participant only for the route (oral, SL, ID) will be halted if any of the following criteria are met. The study will be halted, and all further vaccine administration will be halted for DSMB review/recommendation if any of the following criteria are met for each route of administration:

- Any participant experiences vaccine-related SAE (e.g., excluding trauma or accident) from the time of the first study vaccination through the participant's last study visit.
- Any participant experiences an injection site necrosis within 7 days of vaccination.
- Any participant experiences an anaphylactic reaction related to vaccine occurring within 24 hours after vaccination.
- Any participant experiences urticaria, laryngospasm, bronchospasm, or anaphylaxis determined to be related to vaccine and within 7 days of vaccination.
- Any participant experiences facial nerve neuropathy, within 28 days of vaccination, confirmed by an investigator and determined to be related to vaccine.
- Any participant experiences a death for any reason excluding trauma or accident.

In addition, the study will be halted if two or more participants in the same cohort or three participants across all cohorts within a route of administration (who received at least one dose of study product) experience:

- The same severe (Grade 3) study vaccine-related local solicited event,
- The same severe (Grade 3) study vaccine-related systemic solicited event,
- The same severe (Grade 3) study vaccine-related clinical laboratory test,
- The same severe (Grade 3) study vaccine-related vital sign, or
- Any other severe (Grade 3) AE of the same system organ class

Exceptions to this would be:

- If there are obvious and acceptable physiological explanation for a Grade 3 abnormality (example, grade 3 hematuria in menstruating females)

Once a halting rule is met, further dosing of the respective route will cease, but follow-up visits may continue. An *ad hoc* DMID DSMB meeting and local DSMB meeting will be convened to discuss the halting event. If, following review by both the DMID DSMB and local DSMB, this is deemed acceptable to restart the study, the study will resume, upon DMID's approval and authorization.

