9.6.1 DMID DSMB

The DMID DSMB is convened by authority of DMID and is advisory to DMID and the study team. The DMID DSMB must consist of at least three voting members including a biostatistician experienced in statistical methods for clinical trials and a clinician with relevant expertise. Selection of DMID DSMB members should include consideration of clinical trials experience, relevant expertise, prior DSMB service and absence of significant conflict of interest. DMID is responsible for deciding whether consultancies or the financial interests of the members materially affect their objectivity. Members will notify DMID promptly if a change occurs that may create a potential conflict of interest.

The DMID DSMB will operate under the rules of a DMID-approved charter that will be reviewed and finalized following the organizational meeting of the DSMB. The DMID DSMB Charter serves as the standard operating procedure and defines the primary responsibilities of the DSMB, its membership, the purpose and timing of its meetings, data to be reviewed, and procedures for ensuring confidentiality and proper communication. The following times are the proposed scheduled meetings of the DMID DSMB:

- First/Organizational DMID DSMB meeting –The first meeting of the DMID DSMB will be primarily organizational and to review the study protocol, safety data shells, and frequency of scheduled meetings. This meeting will occur prior to the initiation of study enrollment.

Second Scheduled DMID DSMB meeting – to review the available safety data through 7 days post-third dose of vaccine for cohorts A-F prior to progressing to cohorts G-I, and make a recommendation whether to proceed.

- Third Scheduled DMID DSMB meeting – to review to aggregate safety data through 28 days post-third dose of vaccine for all nine cohorts (can be before database lock).
- Final DMID DSMB meeting - 6 to 8 months after clinical database lock to review the cumulative unblinded safety and efficacy data for the study. The data will be provided in a standard summary format. The DSMB may be asked to provide recommendations in response to questions posed by DMID.

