9.6.3 Local DSMB

The icddr,b has its own regulations and standards for safety oversight, which are independent from the DMID DSMB. The Ethical Review Committee (ERC) of icddr,b will arrange for the formation of a local DSMB for this study. The local DSMB is an independent safety oversight body from the DMID DSMB. The membership of the local DSMB consists of at least 2 members from the ERC, as well as 1-2 members from icddr,b who are not the study investigators (~4-5 members); there may also be 1-2 external members (experts) invited to participate in the local DSMB review—thus there are typically 5-6 individuals participating in the local DSMB for a particular study. The study site PI, together with the key investigators, is expected to formally present the study safety data directly to the local DSMB at specified time points during the conduct of the study. The safety data will be generated from web-reports that are updated daily in the electronic data system.

The first anticipated time for a local DSMB review will be prior to initiation of the study and will be followed by meetings for presentation of safety results as soon as it becomes available after the completion of the 7 days follow up visits after the third dose of vaccine for each dosage and route of administration cohort (cohort A-I). Following each local DSMB meeting, a recommendation will be provided to proceed with the next cohort. *Ad hoc* local DSMB meetings will be convened whenever there are any unexpected safety events. Following completion of the study, a final DSMB meeting is held to update the committee on the results.

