11.3 Planned Interim Analyses

11.3.1 Safety Review

There is no formal statistical interim analysis based on the safety data. The DMID DSMB will review all safety data through 7 days after the third dose of vaccine from Cohorts A through F, prior to making a recommendation to DMID on proceeding to Cohorts G, H, and I. Data for review will have any outstanding queries resolved but the database will not be locked for this review. The DMID DSMB will advise DMID of its findings. If a halting rule is reached, more frequent meetings may be held. The DMID DSMB will be notified when the decision is made to progress to the next cohort.

A local DSMB will also review safety data and will provide a recommendation with enrollment and vaccination of the next successive dosage and route of administration cohort.

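### SAP bilirubin tables have no row for the only scheduled post-vaccination draw that was made (Cohort D, Day 36) and carry Day 57 rows that the protocol does not schedule

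*Protocol*

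**What the plan says.** Protocol 7.1 includes bilirubin in the screening labs. After vaccination it is scheduled once. The Visit 6 list in Protocol 7.3.5 reads "2 mL for clinical safety labs: ALT (also known as SGPT), total bilirubin, and creatinine", and Protocol 8.2.1 repeats it: "2 mL of blood will be collected at visit 6 (7-days post-third dose of vaccine) for ALT, serum bilirubin, and creatinine". The Visit 7 list in Protocol 7.3.6 has no bilirubin: "2 mL for clinical safety labs: CBC with differential for WBC, Hg, ANC, platelets; creatinine, albumin, and ALT". Visits 8 and 9 have no safety labs.

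SAP 15 records that the local DSMB asked for bilirubin at screening and Visit 6, and for ALT and creatinine at Visit 6. It says that these were not obtained in Cohorts A to C and that Visits 6 to 9 did not take place in Cohort E. SAP 9.6 states, in the past tense, that every chemistry and hematology parameter was measured at baseline and Day 57 (Day 71 for intradermal), with ALT, creatinine and bilirubin also at Day 36 (Day 50).

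Table 146 (bilirubin by grade) has baseline, 28-day and maximum-severity rows. Table 150 (bilirubin summary statistics) has baseline, 28-day and 28-day-change rows. Figure 260 plots Cohort D bilirubin at baseline, Day 36 and Day 57.

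On the escalation review, Protocol 4.1 convenes the DMID DSMB after Cohort F to "review all the safety data (clinical labs and reported events) collected in the seven days after the third vaccination in each cohort". Protocol 9.6.1 and 11.3.1 use the same cut. Protocol 11.2 describes the same review as one of cumulative data, held once Cohorts A to F have reached 7 days after dose 3. One Protocol 9.5 halting rule is "The same severe (Grade 3) study vaccine-related clinical laboratory test", met by two participants in a cohort or three in a route.

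**The concern.** The bilirubin tables appear to be built on the wrong visit. They report a time point at which the protocol schedules no bilirubin and have no time-point row for the one at which it was drawn. The Visit 6 labs were added at the request of a safety board, so a study-report reader would look for exactly that result. If the shells are programmed as drawn, the Cohort D Day 36 mean, spread and change from baseline have no place in the summary table. The 28-day rows would be empty or filled from an unscheduled source, and SAP 9.6 would describe collection that SAP 15 says did not happen.

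The secondary question is scope. Read alone, the 7-day wording in Protocol 4.1, 9.6.1 and 11.3.1 could be taken to define a laboratory review that has no scheduled blood count or albumin behind it.

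**Working it through.** **1. Which bilirubin draws exist.** Protocol 7.1, 7.3.5 and 7.3.6 set against SAP 15:

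| Cohort | Screening | Visit 6 | Visit 7 |
|---|---|---|---|
| A, B, C | not obtained | not obtained | not scheduled |
| D | obtained | Day 36 | not scheduled |
| E | obtained | visit not conducted | not scheduled; visit not conducted |

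The entries for D, and for E at screening, are inferred: SAP 15 names only Cohorts A to C as lacking the added labs. Cohorts F to I were not enrolled. One scheduled post-vaccination draw remains, Cohort D Day 36, with a target of 12 vaccinees and 3 placebo.

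**2. Rows of Table 150.** 8 baseline + 6 at 28 days + 6 change at 28 days = 20, of which 6 + 6 = 12 are post-baseline. All 12 are for Day 57, so 0 of 12 match a protocol-scheduled bilirubin draw. Of the 8 baseline rows, 4 (Cohorts A, B, C and oral placebo) have no screening value. The pooled sublingual placebo row can hold only Cohort D's placebo recipients (target 3 of 6).

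**3. Rows of Table 146.** 8 baseline + 6 at 28 days + 8 maximum severity. None of the 6 rows at 28 days has a scheduled draw. There is no 7-day row.

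**4. Comparison tables.** Tables 143 and 147 (creatinine) and 144 and 148 (ALT) have a Cohort D 7-day block, and 147 and 148 add change from baseline. Table 142 (any chemistry) has a Cohort D 7-day block whose footnote excludes only albumin, so bilirubin belongs to that visit. There is no oral bilirubin figure, and Figure 260 is limited to Cohort D. The figures therefore already reflect the missing cohorts, which suggests a slip in the table shells.

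**5. Where Cohort D Day 36 values would appear.** Table 142 (7-day and maximum rows), Table 146 (maximum-severity row only), Figure 260, Listing 23, and Table 140 if abnormal. Table 150: nowhere.

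**6. Grades.** SAP 3.3 sends laboratory grading to Table 8, which shows no bilirubin line in the text available. Protocol Appendix C has one (Grade 1: 1.1 to <1.6 × ULN; Grade 2: 1.6 to <2.6; Grade 3: ≥2.6). Tables 142 and 146 need it.

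**7. Secondary point: laboratory coverage at the 7-day review.** The plan states no coverage figure. Its only numbers for this review are the zero-event bounds in Protocol 11.2. From 1 − 0.025^(1/n), n = 10, 20 and 60 give 30.8%, 16.8% and 6.0%, as stated.

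Appendix C grades 8 analytes: WBC, ANC, hemoglobin, platelets, creatinine, ALT, albumin and bilirubin. Visit 6 covers 3. The other 5 are first drawn after vaccination at Visit 7, 28 − 7 = 21 days later. With visit windows the gap runs from (28 − 3) − (7 + 1) = 17 to (28 + 3) − (7 − 1) = 25 days.

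At the planned review before Cohorts G to I, Visit 7 labs for Cohorts A to E would already exist. An intradermal participant takes 21 + 21 + 7 = 49 days from first dose to Visit 6, against a 21-day gap for Cohort E. The margin is at least 49 − 21 = 28 days (extreme windows: 44 − 25 = 19), assuming Cohort F starts no earlier than Cohort E's last Visit 6.

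The chance that one analyte yields two or more Grade 3 results among 12 vaccinees, 1 − (1−p)^12 − 12p(1−p)^11, is 0.6%, 2.3%, 11.8% and 34.1% at assumed true rates p of 1%, 2%, 5% and 10%.

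**The case against.** The best defence on bilirubin is that no data are lost. Individual values are listed, grades enter Table 146's maximum-severity row and Table 142's 7-day row, and Figure 260 plots Day 36. That stands. A reader might infer that the report would leave out the results the local DSMB asked for, and the documents do not support that. What remains is a missing time-point row in two shells, which costs information mainly in Table 150.

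A reader might also infer that the 28-day rows must be empty. That is not established either. SAP 9.6 says all parameters were measured at Day 57, and Protocol 8.2.1 allows for results from tests run in a panel without being required. SAP 9.6 cannot settle the matter, because it conflicts with SAP 15 for Cohorts A to C and E. The data must be checked.

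On scope, the tempting reading is that a dose level could be cleared with existing Visit 7 labs shut out of the review. The documents do not support it. Protocol 4.1 has the coordinating center supply cumulative safety data for within-route escalation, and Protocol 11.2 gives the DMID DSMB review the same scope. The laboratory rule in Protocol 9.5 has no time limit, so qualifying Visit 7 results halt the route whenever they arise. Any safety concern blocks escalation. SAP 4.4.4 reports earlier US use of these doses without safety signals.

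Nor were the missing 7-day labs for the A-to-B and C-to-D decisions hidden, since SAP 15 discloses them. SAP 6.6.1 says the review before Cohorts G to I was never held. The scope point is therefore one of inconsistent wording and design preference.

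**Conclusion.** The bilirubin shells are wrong as written. Tables 146 and 150 have no 7-day row for the only scheduled post-vaccination bilirubin that was made, all 12 post-baseline rows of Table 150 refer to a visit with no protocol-scheduled bilirubin, and 4 of its 8 baseline rows have no screening value. SAP 9.6 and Figure 260 do not agree with the protocol and SAP 15. The practical loss is the Day 36 summary and change from baseline in one cohort (target 15 participants). This rests on the protocol schedule and on SAP 15 being the accurate account of collection. The Table 8 point depends on the source file.

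The mismatch between the 7-day wording in Protocol 4.1, 9.6.1 and 11.3.1 and the cumulative wording in 11.2 is secondary. It matters only if the study resumes or its design is reused. The 3-of-8 count is exact; the detection probabilities rest on assumed rates. Overall severity is minor.

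**What to change.** For the study report:

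- Add a Cohort D 7-day post-dose-3 block (vaccine and placebo) to Tables 146 and 150, with change from baseline in Table 150, following Tables 143 and 147. This is two lines in Table 146 and four in Table 150.
- Mark bilirubin as not collected at screening and Visit 6 for Cohorts A to C, and footnote that the sublingual placebo row contains Cohort D only.
- Check the database for any Day 57 bilirubin. If there is none, remove the 28-day rows and drop Day 57 from Figure 260. If there is some, keep them and state the source.
- Correct SAP 9.6 to agree with SAP 15.
- Copy the Appendix C bilirubin grades into Table 8 if the source file lacks them.

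The cost is a few shell lines, one data query and a text correction.

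Only for resumption or reuse: reword Protocol 4.1, 9.6.1 and 11.3.1 to match 11.2. Seven days after dose 3 would then be the minimum follow-up for the latest cohort, and the package would include every Visit 7 lab available at the cut-off. This adds no waiting, because it uses data in hand; Protocol 9.6.3 says of the local DSMB reports, "The safety data will be generated from web-reports that are updated daily in the electronic data system".
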